8.4.1 Relationship of SAE to Study Drug

The relationship of each SAE to the study intervention should be characterized using one of the following terms in accordance with CHOP IRB Guidelines: definitely, probably, possibly, unlikely or unrelated.

Type of Unanticipated Problem	Initial Notification (Phone, Email, Fax)	Written Report
Internal (on-site) SAEs Death or Life Threatening	24 hours	Within 2 calendar days
Internal (on-site) SAEs All other SAEs	7 days	Within 7 business days

Unanticipated Problems Related to Research	7 days	Within 7 business days
All other AEs	N/A	Brief Summary of important AEs may be reported at time of continuing review

8.5 IRB Notification of SAEs and Other Unanticipated Problems

The Investigator will promptly notify the IRB of all on-site unanticipated, serious Adverse Events that are related to the research activity. Other unanticipated problems related to the research involving risk to subjects or others will also be reported promptly. Written reports will be filed using the eIRB system and in accordance with the timeline below. External SAEs that are both unexpected and related to the study intervention will be reported promptly after the investigator receives the report.

8.5.1 Follow-up report

If an SAE has not resolved at the time of the initial report and new information arises that changes the investigator's assessment of the event, a follow-up report including all relevant new or reassessed information (e.g., concomitant medication, medical history) should be submitted to the IRB. The investigator is responsible for ensuring that all SAE are followed until either resolved or stable.

8.6 Investigator Reporting of a Serious Adverse Event to Sponsor

Not applicable.

8.7 Medical Emergencies

These subjects are either pregnant mothers or newborns undergoing cardiac surgery requiring postoperative cardiac intensive care. Maternal Fetal Medicine professionals in the Center for Diagnosis and Treatment will be responsible for the care of pregnant subjects in the event of medical emergencies. Cardiac surgical, medical, anesthesia, and nursing professionals in the Cardiac Center will be responsible for the care and treatment of these infants in the event of medical emergencies.

9 STUDY ADMINISTRATION

9.1 Treatment Assignment Methods

9.1.1 Randomization

The study biostatistician, [name], will generate a block randomization schedule based on stratification by fetal CHD diagnosis: TGA, HLHS, and other CHD. The randomization schedule will be based on equal allocation of subjects to the progesterone and placebo arms within each block. The schedule will be generated using variable block sizes. Upon confirmation of eligibility in the DMS, the randomization module will be programmed to generate a randomization number that corresponds to a unique kit number of progesterone or placebo treatment. This kit number will be used to distribute treatment.

9.1.2 Blinding

The study biostatistician, [name], will generate a block randomization schedule based on stratification by fetal CHD diagnosis: TGA, HLHS, and other CHD. The randomization schedule will be based on equal allocation of subjects to the progesterone and placebo arms within each block. The schedule will be designed so that the block size is not fixed. Upon

confirmation of eligibility in the DMS, the randomization module will be programmed to generate a randomization number that corresponds to a unique kit number of progesterone or placebo treatment. This kit number will be used to distribute treatment.

9.1.3 Unblinding

Unblinding can occur if the PI instructs the Investigational Pharmacy to reveal this information. A direct request from the PI to Investigational Pharmacy must be documented.

9.2 Data Collection and Management

The following non-research data sources will be queried for demographic and medical data etc.: ChartMax, CardiolMS, EPIC, CardioAccess, CompuRecord, PC4 and other applicable clinical databases.

1. Confidentiality: The following methods will be utilized to ensure confidentiality of research study data [including source documents, case report forms, & data in computerized systems]
 - a. Access to identifiable study data, databases containing identifiers, and systems will be limited to study personnel who have valid CHOP enterprise password and login, who have been designated by the PI and approved by the IRB, and who are using a computer that is connected to the internal CHOP network.
 - b. Password-protected data base will be utilized
 - c. Data files copied to removable disk drives will be encrypted
2. Security: Data will be entered, cleaned and maintained in a password-protected research database in the located in the Cardiothoracic Surgery suite. All data management applications, databases, and data are hosted on secure servers in the offsite CHOP data center, hosted by a commercial provider. Physical access to the data center is monitored, logged, controlled and limited to approved CHOP personnel. System administration and support is provided by CHOP Research Information Systems. Servers and the Case Report Application are actively monitored 24x7x365 and replicated between two geographically separate fully redundant data centers. Server backup at the file system level is performed multiple times per day, and a multi-day real-time accessible rolling archive will be maintained. After seven days, data will be compressed and moved to an online archive that may be accessed upon documented request to Research Information Systems. System and data recovery are accomplished through documented standard operating procedures.
3. Anonymization, de-identification or destruction: Identifiers will be kept in conjunction with the study identification number for the purposes of the 18 month follow-up and future investigation.

9.3 Confidentiality

All data and records generated during this study will be kept confidential in accordance with Institutional policies and HIPAA on subject privacy and that the Investigator and other site personnel will not use such data and records for any purpose other than conducting the study. Safeguards are described under Data Collection and Management (9.2).

9.4 Regulatory and Ethical Considerations

9.4.1 Data and Safety Monitoring Plan

The purpose of this Data and Safety Monitoring Plan is to ensure the safety of research participants and the integrity of the research data.

Safety of Research Participant:

Protection of the rights and welfare of subjects and their families will be maintained during the recruitment, consenting process, and study participation. [name] and his study team have over a 15-year experience in recruiting and enrolling patients for research studies in the Cardiac Center. Subject privacy and confidentiality will be maintained as described in Section 8.3. All research responsibilities delegated by the principal investigator to study team members will be carried out in accordance with the protocol, federal regulations, federal, state and local laws and institutional policies and procedures. The study team has two research nurses, one of which is a Certified Clinical Research Coordinator (CCRC). If any the results of research procedures appear to be important for immediate clinical care, these results will be provided to the Principal Investigator ([name]) of the study who will forward the information to the subject's surgeon, cardiologist and/or primary physician.

The Principal Investigator ([name]) and Co-Investigators (Drs. [name], [name], [name], [name], and [name],) will be responsible for reviewing subject enrollment data, maternal events, and clinical event data as described in Section 7.4 every 2 weeks. [name] is a pediatric cardiothoracic surgeon. [name] is a pediatric neurologist. Drs. [name] and [name] are fetal cardiologists. Drs. [name] and [name] are experts in Maternal-Fetal Medicine. Data will be reviewed for adverse events and actions appropriate to the event will be initiated.

Data Safety Monitoring Board (DSMB):

9.4.2 Risk Assessment

Progesterone Therapy

The existing evidence suggests that progesterone therapy is associated with potential benefits to the mother and fetus in singleton pregnancies, with greater than minimal risk.

Maternal Risks

Multiple reviews have found that there do not appear to be any significant maternal or fetal risks associated with progestin therapy. , ,^{40, 42, 43, 45} The lower blood levels after vaginal administration have been associated with a lower prevalence of systemic side effects.^{3, 5} The most common side effect of vaginal progesterone administration is local irritation. A recent randomized trial of Crinone vaginal gel vs. intramuscular progesterone during ART showed that patient satisfaction in terms of ease of administration, convenience of administration and discomfort was significantly greater for patients receiving Crinone.⁹⁰ Additional supportive evidence of safety and efficacy is found in the 2011 FDA Advisory Committee Briefing Book. (Attached to application)

Stopping Rule

In previous studies, the vaginal progesterone gel has been well tolerated with few adverse effects. The most common effect is vaginal irritation which will be treated with sitz baths; and for severe cases a low potency topical steroid cream (hydrocortisone 1 % cream). If a woman goes into preterm labor, this will be treated according to standard clinical protocols. We anticipate that need to terminate study drug prior to 39 weeks or delivery (if earlier) will be infrequent.

Risks to Fetus and Newborn

The effects of progesterone on perinatal outcomes and the neonate are of special interest. A recent meta-analysis attempted to quantify the effect of progesterone therapy for the prevention of preterm birth on perinatal outcomes.⁴² The authors concluded that progesterone administration in singleton pregnancies at risk for preterm birth improves perinatal outcomes, but may actually have adverse effects in multiple pregnancies.⁴² Other reviews have also found that there do not appear to be any significant maternal or fetal risks associated with progestin therapy.⁴⁵ Longer term outcomes have also been evaluated.³⁶ Surviving children from a trial of 17-OHP-C vs. placebo to prevent preterm birth underwent physical examination and developmental screening at 48 months of age. Progesterone therapy was not associated with any adverse physical or neurodevelopmental sequelae.³⁶

Risk Assessment for Pre-Natal Evaluations

Fetal Magnetic Resonance Imaging:

All of the fetal brain MRI examinations performed in this study will be during the 25th week GA or beyond. No MRI will be performed in the first half of pregnancy or embryonic period. None of the studies will be performed with gadolinium contrast administration. None of the studies will be done with sedation or general anesthesia. General MRI safety guidelines for metallic objects in the MRI environment will be monitored as part of standard practice by the MRI technologists and radiology nursing staff. At the Children's Hospital of Philadelphia, clinical fetal MRI studies are routinely and safely performed at 16 weeks GA and beyond. To avoid conflict of interest concerning decisions about termination or continuation of a study, the anesthesiologist for the research MRIs will not be a member of the study team.

There are no verified or scientifically proven additional side effects of clinical MRI on human fetuses within the safety limits of performing MRI studies. The FDA has specific limits on the amount of energy deposition by MRI which is built in as a fail-safe warning mechanism

on all of the MRI systems at CHOP, which used for all patients. There is little direct scientific evidence of harmful effects with short-term exposure to high static magnetic fields.⁹¹ Two to three decades of practice generally supports this widely-held belief.^{78, 79} FDA guidelines now classify MRI devices as “nonsignificant risk” when neonates (infants less than one month of age) are scanned at a static magnetic field of 4T or less. As a result, it has become widespread routine clinical practice to scan even the youngest premature infants who are stable for transport. Myers and coworkers reported no significant reduction in fetal growth in 74 volunteer subjects exposed in utero to MRI vs. matched controls.⁹² Also the recent practice parameter from the American College of Radiology and the Society for Pediatric Radiology for fetal MRI states, “At this stage, the preponderance of research studies have failed to discover any reproducible harmful effects of exposure of the mother or developing fetus to the 3T or weaker magnetic fields used in the routine clinical MR imaging process.”⁹³ Some MRI sequences are for research purposes and are not FDA approved. However, all the sequences will be below the FDA energy deposition limits and no gadolinium contrast will be used.

A “potential” side effect of the MRI environment is exposure to high sound levels. Baker and associates reported no demonstrable increase in disease, disability, or hearing loss in 20 children examined in utero using echoplanar MRI for suspected fetal compromise.⁹⁴ In a 2010 study, Reeves and colleagues found no evidence that exposure of the fetus to 1.5T MR imaging during the second and third trimesters is associated with an increased risk of substantial neonatal hearing impairment.⁹⁵

Risk Assessment for Post-Natal Evaluations

Transport:

This is a high-risk group of subjects being transported from the cardiac intensive care unit (CICU) to the MRI suite. The risks of transport include exposure to cooling temperatures, dislodging arterial and venous lines and accidental extubation. To accomplish safe transport of subjects, all subject transports will be performed by a team of cardiac anesthesiologists including an attending, a fellow and a respiratory therapist. This team of physicians has a great deal of experience both in transporting high-risk neonates (n>200) to the MRI suite for preoperative and post-operative studies.

Magnetic Resonance Imaging:

MRI is an electromagnetic imaging technique that does not use ionizing radiation such as x-rays to obtain the images; as such there are minimal risks involved with this technique. The Food and Drug Administration (FDA) guideline for average specific absorption ratio (SAR) is 3W/kg over the head for 10min. The SAR level of this CASL sequence, calculated using quasi-static approximation (spherical head model), is 1W/kg on an average head size with radius of 10cm. The SAR level is also automatically calculated and monitored by integrated product program during MR scanning according to the legal requirement value (IEC 60601-2-33, accepted by the US FDA). A mean SAR level (percent of maximal allowable SAR) of 54.5±15.6% (40-80%) was observed on 13 healthy adult subjects (radiology in press paper). The SAR level actually is lower in children and infants than in adults because it is roughly proportional to the square of the head size (radius).⁹⁶ The 3T CASL method is therefore very safe for pediatric imaging.

Sedation for the Pre-Operative MRI:

The pre-operative MRI will be performed during the same anesthetic period as the planned surgery. On the morning of heart surgery, the patient will be induced for anesthesia using published protocols.^{66, 97} Immediately prior to surgery, the patient will be brought to the MRI scanner located between the CICU and the operating rooms. Upon completion of the pre-operative MRI protocol, the infant will be transported to the operating room where the surgery will take place. During transport and the MRI procedure, the patient will be monitored by a team of cardiac anesthesiologist. To avoid conflict of interest concerning decisions about termination or continuation of a study, the anesthesiologist for the research MRIs will not be a member of the study team.

Sedation for the Post-Operative MRI:

For the post-operative MRI procedure, primary consideration will be given toward the possibility of a non-sedated, "sated sleep" protocol. All infants will be transported to and from the MRI scanner by a team of pediatric cardiac anesthesiologists. For a sated-sleep MRI the infant would be held NPO for 3 or 4 hours prior to the study. The subject would be transported awake to the scanner, ear protectors and ECG leads would be placed and the subject swaddled with warm blankets. The infant would then be offered formula/breast milk ad-lib or as recommended by the ICU protocol. When postprandial sleep is achieved the subject is placed in the scanner. The MRI sequences will be run in order of relative importance to the study, with T1 MPR and DWI taking highest priority.

The decision to use the sated sleep protocol will be made by either [name] or [name] and it will be done on a patient-by-patient basis. There are some concerns that may make this procedure untenable: first, the patient must tolerate oral feeds to be eligible for such a protocol; second, agitation in a post-operative infant may cause unsafe increase in blood pressure. The advantages are clear and include primarily decreased risk of respiratory compromise when compared to sedation.

If a "sated sleep" MRI procedure is not an option (if the infant is not tolerating oral feeds, for instance), an individualized sedation protocol will be administered by Cardiac Anesthesia for the post-operative MRI scan. The sedation will follow protocols that have established safety and have been used successfully in the past. The medications used for sedation will be determined by the anesthesiologist responsible for the case but will likely include the use of pentobarbital. All subjects will have heart rate, blood pressure and oxygen saturations monitored throughout the study. Any deviation in oxygen saturations of more than 10% would necessitate the discontinuation of the study and immediate medical evaluation of the subject.

Stopping Rule

Our previous experiences with pre-operative and post-operative MRI suggest that these are safe procedures with our research team. In this study we expect similar results. This notwithstanding, enrollment for this study will be halted temporarily if two subjects experience vital sign fluctuations that require termination of their MRI. Enrollment will not resume until independent review of procedures determines the safety for continuation. All adverse events will promptly be reported to the IRB. All SAEs will be reported to the board within 24 hours of occurrence.

Review of Medical Record

Collecting data from the medical record may increase the risk of breach of privacy and confidentiality. All data and records generated during this study will be kept confidential in accordance with institutional policies and HIPAA on subject privacy and the Investigator and other site personnel will not use such data and records for any purpose other than conducting the study.

Blood Work for Mothers/Fathers

Taking blood may cause some pain, bleeding or bruising at the spot where the needle enters your body. Rarely, taking blood may cause fainting or infection.

Blood Work for Infant

The sample will be obtained from an existing central venous or arterial line, which is associated with minimal risk of pain or complication.

18-month Developmental and Medical Follow-Up

There are no physical risks but toddler-age children may become uncooperative. The Neonatal follow-up team has over 10 years of experience in developmental assessments of infants and children with CHD. Parents and child will remain together throughout this assessment in order to provide support and comfort to the child. Because the early assessment measures for children from birth to 3 are based on play, typically children enjoy these sessions.

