3.1.1 Screening Phase

Potential subjects will be identified by clinically indicated fetal echocardiography in the Fetal Heart Program Clinic by one of the investigators ([name] or [name]). Potential subjects will be screened for eligibility at 24-28 weeks GA by a study nurse using the protocol inclusion and exclusion criteria. Subject permission (informed consent) will be obtained prior to any study related procedures being performed.

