3.1.3 Post-Natal Phase

After birth, the child will undergo clinically indicated evaluation and treatment. Data will be collected from the medical record concerning diagnosis, associated anomalies, medical and surgical management and the hospital course. A blood (either from the cord or from an existing blood drawing line during a hospitalization, routine clinical labwork or at the time of a research draw for a separate study) or saliva sample will be obtained for genetic testing. An early post-natal brain MRI will be obtained on the day of cardiac surgery, during the same anesthetic but prior to surgery. Post-operative brain MRI will be obtained within 10 days of surgery.

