3.3.2 Total Number of Study Sites/Total Number of Subjects Projected

The study will be conducted at a single site, the Children's Hospital of Philadelphia. We plan to enroll sufficient patients to have 80 evaluable patients (40 per treatment group) at the 18 month neurodevelopmental testing. Based on known clinical outcomes for this patient population and experience with other studies with similar follow-up plans, we estimate a 5% early mortality and a further 20% attrition from all causes between hospital discharge and the 18 month evaluation. There may also be dropout prior to birth for a variety of reasons: fetal death, intolerance of therapy, withdrawal from study. We do not have accurate data to estimate this loss. We anticipate needing to enroll 110-130 patients to have a sufficient cohort at 18 months (40 per treatment group), with 60 and 52-56 patients, respectively, per treatment group available for the post-natal and post-operative brain MRIs. Based on current patient

volume in the Fetal Heart Program Clinic, we anticipate there will be 70-75 eligible patients each year. If the consent rate is 65%, we will be able to complete enrollment within 3 years.

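### The post-natal MRI stopping rule pauses enrollment but, as written, not the scans, so it does not reach infants who are already enrolled

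*Protocol*

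**What the plan says.** Protocol 9.4.2 has two paragraphs headed Stopping Rule. The one under maternal risks contains no count and no halt. The one that follows the post-natal sedation text covers the pre- and post-operative MRIs and reads: "enrollment for this study will be halted temporarily if two subjects experience vital sign fluctuations that require termination of their MRI". The restart condition follows: "Enrollment will not resume until independent review of procedures determines the safety for continuation".

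On timing, section 3.1.1 says "Potential subjects will be screened for eligibility at 24-28 weeks GA by a study nurse", and section 3.3.1 starts participation in the same window. Section 3.1.3 says "An early post-natal brain MRI will be obtained on the day of cardiac surgery, during the same anesthetic but prior to surgery", with a second scan within 10 days of surgery. Section 3.4.1 requires the surgery to fall before 44 weeks corrected gestational age.

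On the hazards, the Transport paragraph of 9.4.2 says "The risks of transport include exposure to cooling temperatures, dislodging arterial and venous lines and accidental extubation". For the post-operative scan, "All subjects will have heart rate, blood pressure and oxygen saturations monitored throughout the study". For the individual infant, "Any deviation in oxygen saturations of more than 10% would necessitate the discontinuation of the study and immediate medical evaluation of the subject".

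**The concern.** A halt to enrollment protects participants when enrollment is soon followed by the risky procedure. Here the two are separated by most of the third trimester and the time to surgery. The event that fires the rule is a problem with a scan of a newborn, but the action is to stop approaching pregnant women. The infants next in line for that procedure were enrolled weeks earlier, and the rule does not mention them. After the last mother is enrolled, the rule has nothing left to act on, although scans are still due.

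This matters because section 9.4.4 gives the possible need for sedation in the MRI assessments as its reason for classing the study as greater than minimal risk. The rule is the only numeric study-level pause visible for that component, and section 6.5 plans no interim analysis.

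A second, smaller issue is the trigger. It counts scans ended for vital sign changes, whereas the protocol also names harms that can occur on the way to or from the scanner.

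**Working it through.** **Step 1: what the halt covers.** Both sentences of the rule have enrollment as their subject. The review concerns procedures, but only resumption of enrollment depends on it. I found no visible text that suspends scans in enrolled infants when the rule fires, and none that says they continue.

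**Step 2: accrual rate.** Inputs from section 3.3.2: "we anticipate there will be 70-75 eligible patients each year", a conditional consent rate of 65%, and 110-130 to be enrolled within 3 years.

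- 70 × 0.65 = 45.5 per year; 75 × 0.65 = 48.75 per year.
- Check against the plan: 110 / 48.75 = 2.3 years and 130 / 45.5 = 2.9 years. The stated 3 years is reproduced.
- Per week: 45.5 / 52 = 0.88; 48.75 / 52 = 0.94.

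**Step 3: lag from enrollment to first post-natal scan.** The protocol gives no figure, so this is assumed.

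- Central: enrolled at 26 weeks (mid-window), delivered at about 39 weeks, surgery soon after: 13-14 weeks.
- Short: enrolled at 28, surgery at 37: 9 weeks.
- Long: enrolled at 24, surgery at the 44-week limit: 20 weeks.

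Nine weeks is illustrative, not a minimum. Section 1.5.6 reports that 16% of CHD births at this site were at or before 37 weeks.

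**Step 4: dyads enrolled and awaiting a first scan (rate × lag).**

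| Lag (weeks) | 0.875 per week | 0.9375 per week |
|---|---|---|
| 9 | 7.9 | 8.4 |
| 13 | 11.4 | 12.2 |
| 14 | 12.3 | 13.1 |
| 20 | 17.5 | 18.8 |

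The central estimate is 11-13 dyads, range 8-19, before losses prior to birth.

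**Step 5: scans outside the halt.** Section 3.3.2 expects 60 pre-operative and 52-56 post-operative scans per arm.

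- Total: 2 × (60 + 52) = 224 to 2 × (60 + 56) = 232.
- Per dyad, if 130 enroll: 224 / 130 = 1.72 to 232 / 130 = 1.78.
- Allowing for these losses: 11 × 1.72 = 19 to 13 × 1.78 = 23 scans.
- Without losses: 11 × 2 = 22 to 13 × 2 = 26 scans.

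That gives roughly 19-26 scans, about a tenth of the planned total (19 / 232 = 8%; 26 / 224 = 12%).

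**Step 6: trigger against named risks.** An extubation or line loss that disturbs heart rate, blood pressure or saturation and ends the scan counts. The same event in transit, or after a completed scan, does not count on the wording. Cooling counts only if it shows up as a scan-ending vital sign change; temperature is not in the monitoring list quoted above.

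**The case against.** The strongest reply is that the rule is not the infants' only protection.

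- The saturation limit ends the individual scan.
- The anesthesiologist for the research MRIs is outside the study team, so that decisions to end a scan are not conflicted.
- Adverse events go promptly to the IRB, and serious ones to the board within a day.
- The investigators review events every two weeks and act on them (9.4.1), and they may withdraw subjects for safety (4.5).

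All of this stands. A reader might infer from the rule that infants are left unprotected, or that the protocol directs scanning to continue. The documents support neither: the rule is silent on scans, and an independent review of procedures may have been meant to cover them. The body of the DSMB paragraph in 9.4.1 was also not in the text available to me and may contain a power to pause procedures. What the reply does not supply is a visible study-level pause of scanning. A rule written for this hazard should not depend on powers stated elsewhere.

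A reader might also infer that transport harms are left out of the trigger altogether. They are not: those that end a scan through a vital sign change count, and the rest remain reportable events.

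Finally, the numbers rest on assumptions. A claim that any pause under nine weeks would prevent no scan would be too strong, because earlier births shorten the lag. The mismatch between action and hazard does not depend on the exact count.

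**Conclusion.** The point holds as a mis-targeted rule. On its wording, the halt and the restart condition govern enrollment only. They therefore do not reach enrolled infants awaiting post-natal research scans, and they have no effect after accrual closes. About 11-13 dyads (range 8-19), or roughly 19-26 scans, lie outside a halt at any one time during steady accrual. This rests on the planned eligibility figures, the conditional 65% consent rate, a 13-14 week lag (9-20 illustrated), and between 1.7 and 2 scans per dyad. The conclusion is limited to the visible text.

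The trigger issue is a request for clarification. The documents do not settle whether a transport event that leaves the scan unaffected counts, and they give no event rates from which a different trigger could be judged.

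**What to change.** Amend the Stopping Rule paragraph so that, when it fires, pre- and post-operative research MRIs in all enrolled infants are paused together with enrollment, and both wait for the independent review. Leave the count of two and the individual scan-termination criteria unchanged. If the DSMB text already provides such a pause, a cross-reference is enough.

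Separately, the sponsor should reconcile the trigger with the Transport paragraph by stating whether transport events that do not end a scan count toward it. I propose no new trigger.

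The drafting cost is one paragraph. The data cost is real. The pre-operative scan is tied to the surgical anesthetic, so it cannot be made up later. Infants whose surgery falls within a pause lose TMS, brain volume and PVL data, which are secondary endpoints. A pause is not a remote event: if 1%, 2% or 5% of 120 infants had a terminated scan (assumed rates; the documents give none), the chance of at least two would be 34%, 70% or 98%. The SAP also analyzes MRI completion as an endpoint, so scans missed because of a pause should be recorded as such. The Bayley-III Motor Scale at 18 months is unaffected.
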